Biochemistry. Recent studies in the [name] Laboratory have generated exciting preliminary results showing essential amino acid (EAA) supplementation attenuates quadriceps atrophy and accelerates the return of functional mobility following TKA (37). For patients on EAA, quadriceps atrophy was only -6% & -3% in the operative and non-operative quadriceps, respectively, six weeks after TKA but -18% & -10%, respectively, in patients on Placebo (a 3-fold difference). Of clinical relevance, these patients on EAA were able to maintain strength and demonstrated an accelerated return of functional mobility vs. Placebo, 6 wk post-TKA. At the cellular level, our preliminary results show that EAA supplementation

down-regulated catabolic signaling (FoxO3a) and up-regulated amino acid transporter (SLC36A2), regulated in development and DNA damage response (REDD1) and activating transcription factor 4 (ATF4) expression vs. Placebo. While studies by others have linked these molecules with the insulin like growth factor (IGF-I) and vascular endothelial growth factor (VEGF) (i.e., angiogenesis) pathways, whether they are directly stimulated by EAA supplementation in a clinical population remains unknown. We interpret these positive changes at the cellular level to be responsible for the reduction in muscle loss and, preservation of strength, and explain the acceleration of the return of functional mobility.

Our preliminary fractional synthesis data (FSR) show that older adults respond appropriately to acute ingestion of 20 g of EAA (i.e., similar response to young healthy controls). We also have preliminary FSR data showing that basal rates of muscle protein synthesis are similar between TKA patients ($0.0563 \pm 0.008\%$ /hour) and older healthy control subjects ($0.0566 \pm 0.008\%$ /hour). What is not known is what effect TKA has on muscle protein synthesis and breakdown in response to chronic EAA supplementation (for 1 week prior to, and for 6 weeks post-TKA). We have extensive experience with stable isotope tracer methods to determine fractional synthesis rates (FSR), a direct measure of muscle protein synthesis (31-35, 39-41, 50, 113, 114). However, in order to determine mechanisms, and link cellular changes in anabolic and catabolic pathways with atrophy (Placebo) and atrophy prevention (EAA) we must also quantify muscle protein breakdown.

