Power analyses. For our power calculations, we have assumed a Type I error rate (α) of $.05$, two-tailed. We based power calculations on effect sizes (d) that we derived from analysis of preliminary data preliminary data and prior studies (10, 30, 32, 33, 36, 41, 51, 113). We calculated d as the standardized mean difference between treatment conditions at follow-up: $d = (x_C - x_T)/S$, where x_C represents the primary outcome mean in the Placebo and EAA conditions and S is the pooled standard deviation, after adjusting x for pretest scores and covariates (sex, tourniquet time, age, body mass index, fat/carbohydrate/protein intake).

We propose to enroll **40 total subjects for Aim 1** who are retained through protocol completion (20/group, EAA and Placebo, randomized to either 1 week or 2 week post-operative biopsies), and **80 total subjects** (40/group, EAA and Placebo) **for Aim 2** who are retained through protocol completion to account for possible attrition and to ensure sufficient power to test the hypotheses that EAA therapy up-regulates basal levels of muscle protein synthesis, and reduces post-operative atrophy bilaterally, preserves quadriceps strength, and improves functional mobility relative to a Placebo condition.

Effect sizes. Effect sizes were as follows: (a) Cell and FSR data: REDD1 $d = 1.24$, SLC36A2 $d = 1.27$, and FSR $d = 1.51$ (FSR calculated from mean change from baseline). The mean effect across outcomes was $d = 1.37$, reflecting large effects. (b) Physiological and functional data (percent change from Baseline to 6 wk): operative quadriceps volume $d = 1.52$, and isometric strength $d = .90$; non-operative quadriceps volume $d = 1.05$, and isometric strength $d = .66$; timed up-and-go test $d = 1.03$, timed stair ascent $d = 1.08$, timed stair descent $d = 1.13$, and six-minute walk test $d = .70$. Mean effect size was $d = 1.01$, reflecting large effects.

Power calculations. Power calculations were based on the sample size and minimally detectable ES (MDES) as follows:

- **Aim #1:** For a sample size of 20 completed subjects/group (10/group for metabolic studies, however, EAA vs. Placebo = 20 total EAA and 20 total Placebo). Aim 1, proposed study can detect

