ESs of $d > 1.10$ with 85% power, assuming no pretest covariate, and the minimally detectable ES drops to 0.95 or 0.72 with pretest covariates of $r = .50$ or $.75$, respectively. The preliminary results show ESs averaged 1.37 for Cell and FSR outcomes, and all exceeded .95. The proposed study would thus have the power to detect anticipated condition effects for Cell and FSR outcomes in Aim 1 with 10 subjects per condition. We can also detect moderation effects for sex if the associated interaction accounts for at least 21% to 31% of the variance, assuming covariate of $r = .75$ or $.50$, respectively.

- **Aim #2:** For a sample size of 40 completed subjects/group (EAA and Placebo), the proposed study can detect ESs of $d > .79$ with 85% power, and the minimally detectable ES drops to .68 or .52 with pretest covariates of $r = .50$ or $.75$, respectively. Preliminary results show an average ES of $d = 1.01$ across all Aim 2 outcomes, so this study will have power to detect anticipated physiological and functional effects with 40 subjects per condition. We can detect condition-by-sex moderation effects if the associated interaction accounts for at least 12% to 19% of the variance, assuming covariate of $r = .75$ or $.50$, respectively. The tests of sex-by-condition interactions in both aims are likely underpowered for some important effects, so we will also consider the size of the effect, even if not statistically significant, as an indicator of potentially important sex-related differences.

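### The mean effect of 1.37 behind Aim 1's power claim does not match its three printed components, which average 1.34, and the plan does not say whether the FSR component is an EAA-Placebo contrast

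*Combined protocol and SAP*

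**What the plan says.** All of this is in the combined protocol and SAP.

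- **Data Analysis, Power analyses.** On the error rate: "we have assumed a Type I error rate (α) of $.05$, two-tailed". On the effect measure: "We calculated d as the standardized mean difference between treatment conditions at follow-up". The effects are said to come from preliminary data and a list of prior studies.
- **Data Analysis, Effect sizes.** The Cell and FSR list has three entries: REDD1 1.24, SLC36A2 1.27 and FSR 1.51. The last is annotated "FSR calculated from mean change from baseline". The mean is printed as 1.37.
- **Data Analysis, Power calculations, Aim #1.** The sample is 20 completed subjects per group, with 10 per group for the metabolic studies. The detectable effects are given as "ESs of $d > 1.10$ with 85% power, assuming no pretest covariate", and then "the minimally detectable ES drops to 0.95 or 0.72 with pretest covariates of $r = .50$ or $.75$, respectively". The argument continues: "The preliminary results show ESs averaged 1.37 for Cell and FSR outcomes, and all exceeded .95". From this the plan concludes that 10 per condition are enough for the Cell and FSR outcomes.
- **Preliminary Studies, Biochemistry.** The FSR data described are an acute response ("older adults respond appropriately to acute ingestion of 20 g of EAA", set against young controls) and basal rates in arthroplasty patients against healthy older controls. The section then says: "What is not known is what effect TKA has on muscle protein synthesis and breakdown in response to chronic EAA supplementation".

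**The concern.** The mean is a premise of the power conclusion and should follow from the values printed beside it. It does not.

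FSR is also the largest of the three values and the only one singled out as computed in another way. The plan defines d as a difference between arms at follow-up. The annotation does not say whether the FSR figure is such a difference, and the preliminary synthesis data described are not EAA-versus-Placebo data after surgery.

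This matters because protein synthesis is the lead question of Aim 1. If the anticipated effect or the detectable effect is stated too favourably, a null synthesis or signalling result from 10 per group could be read as evidence of no effect when the comparison had limited power.

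**Working it through.** **1. The printed mean.** The inputs are the three values under Effect sizes.

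(1.24 + 1.27 + 1.51)/3 = 4.02/3 = 1.340. Allowing for rounding of the inputs, the range is 1.335 to 1.345, so 1.37 is not reproduced.

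Other summaries of the three values do not give it either: median 1.27, geometric mean 1.335, root mean square 1.345, and the average of the cell mean and FSR (1.255 + 1.51)/2 = 1.383. The nearest is REDD1 and FSR alone, (1.24 + 1.51)/2 = 1.375, which drops a listed outcome. To reach 1.37, FSR would have to be 3 × 1.37 − 2.51 = 1.60, or an unprinted fourth value would have to be 4 × 1.37 − 4.02 = 1.46.

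The neighbouring physiological list shows that simple averaging is the plan's method: (1.52 + 0.90 + 1.05 + 0.66 + 1.03 + 1.08 + 1.13 + 0.70)/8 = 8.07/8 = 1.009, printed as 1.01.

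Without FSR the mean is (1.24 + 1.27)/2 = 1.255, or 1.26.

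**2. The detectable effect.** This is a two-sample t test with two-sided alpha .05. Power is the probability that a noncentral t exceeds its critical value, with noncentrality d/√(1 − r²) × √(n/2) and 2n − 2 degrees of freedom (one fewer with a covariate). Solving for 85% power:

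| n per group | no covariate | r = .50 | r = .75 |
|---|---|---|---|
| Plan, as printed | 1.10 | 0.95 | 0.72 |
| 10 | 1.42 | 1.23 | 0.94 |
| 16 | 1.095 | 0.949 | 0.725 |
| 20 | 0.97 | 0.84 | 0.64 |

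The plan's figures correspond to about 16 per group (about 15 with the normal approximation: 1.094, 0.948, 0.724). They match neither of the two sizes that the plan names.

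**3. Power at 10 per group.** Example: REDD1 without a covariate has noncentrality 1.24 × √5 = 2.77 on 18 degrees of freedom, which gives 74.6%.

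| d | no covariate | r = .50 | r = .75 |
|---|---|---|---|
| 1.24 (REDD1) | 74.6% | 85.5% | 97.6% |
| 1.27 (SLC36A2) | 76.6% | 87.1% | 98.1% |
| 1.51 (FSR) | 89.1% | 95.6% | 99.8% |
| 1.37 (printed mean) | 82.6% | 91.5% | 99.2% |
| 1.34 (actual mean) | 80.9% | 90.3% | 98.9% |
| 1.255 (without FSR) | 75.6% | 86.3% | 97.9% |

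At 20 per group without a covariate, every value in the table has about 97% power or more.

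Without a covariate, FSR is the only printed value above the 1.42 threshold at 10 per group, and it is the one whose origin is unclear. The pretest correlations quoted as examples under Analysis of covariance are for muscle volume, strength and stair descent. None is given for FSR or for the cell outcomes.

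**The case against.** The strongest reply is that the slip changes little. Moving from 1.37 to 1.34 costs 82.6 − 80.9 = 1.7 points of power at 10 per group. The plan also relies on each effect exceeding .95, and each printed value does. With the normal approximation, power at d = 1.34 and 10 per group is 85.0%. At 20 per group power is ample. The recruitment text for Aim 2 says that the first part was completed in 2016, so the design of Aim 1 cannot change. All of this stands as to size. However, the .95 benchmark belongs to about 16 per group. At 10 per group with r = .50 it is 1.23, which REDD1 clears by only 0.01.

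It is also fair to say that the mean may be right and a component misprinted, or the list incomplete: Preliminary Studies also reports FoxO3a and ATF4, for which no d is printed. The request is therefore to reconcile the figures, with 1.34 as the value that follows from the text as it stands.

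A reader might go further and infer that FSR 1.51 is a within-group change, so that no EAA-Placebo effect lies behind the power claim. The documents do not support that. The annotation fits an EAA-Placebo difference in change equally well, and that is the comparison Data Analysis sets for Aim 1. The physiological effects in the same paragraph are also labelled as change from baseline. The effect sizes draw on cited studies that cannot be inspected here.

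Nor is all the synthesis evidence acute. The Introduction cites chronic supplementation in healthy older adults, and Investigational Supplement describes a 3-day leucine study. Neither is described as an EAA-Placebo comparison after arthroplasty.

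**Conclusion.** The point holds in a limited form. The printed mean of 1.37 does not follow from its components, which average 1.34. Whether FSR 1.51 is a between-arm contrast is not stated and should be; it is an open question, not a demonstrated error.

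The numerical correction alone is worth under 2 points of power. The larger consequence is that at 10 per group, without help from a pretest covariate, the detectable effect of 1.42 exceeds the actual mean and both cell effects. REDD1 and SLC36A2 then have about 75% and 77% power. They reach about 86% and 87% if r = .50 holds, and the plan documents no such correlation for these outcomes.

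These figures assume a two-sample t test at two-sided alpha .05, equal groups, and a covariate that reduces the error SD by √(1 − r²).

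It is tempting to convert d into %/hour with the basal rate of 0.0563 ± 0.008 in Preliminary Studies. That is not supported: the ± is not labelled as an SD, and it describes a basal level, which need not be the analysed quantity.

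**What to change.** 1. Under Effect sizes and under Power calculations for Aim #1, change 1.37 to 1.34, or correct the component that is misprinted or missing.
2. State which data FSR 1.51 comes from and whether it is an EAA-Placebo contrast. If it is not, take it out of the list, give the mean as 1.26, and say that the list holds no between-arm estimate for synthesis.
3. Restate the effect detectable with 85% power in d units at the sample sizes used (no covariate / r = .50 / r = .75): 1.42 / 1.23 / 0.94 at 10 per group and 0.97 / 0.84 / 0.64 at 20 per group. Say which row applies to each outcome, and that the two cell effects reach 85% at 10 per group only with a pretest correlation of about .50 or more.
4. Give no detectable difference in %/hour unless ±0.008 is confirmed as the SD of the analysed quantity.

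The cost is rewording and a slightly less favourable stated figure. Recruitment and procedures are unaffected. The benefit lies in how Aim 1 results are interpreted and reported, including the report to the FDA required under the IND.

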Patient history, body composition, strength and functional data, blood samples, and muscle & fat tissue samples will be obtained specifically for research purposes. Coded data will be stored on computers that are password protected and in locked offices. Data on paper will be stored in files in a locked file cabinet (printouts) and computers in a key-code-access-only lab in a badge-access building. All data and material collected will be coded. Codes linked to subjects' names will be stored in the PI's office (key lock) on a MacPro with password protection and backed up to a protected and locked time capsule 2T external storage device. All MR images will be transferred as DICOM files to [name] laboratory via encrypted electronic data transfer protocol currently established by the collective efforts of our IT department at the University of Oregon.

All research personnel will have access to the coded data, and coded blood and coded tissue specimens. Only the PI, physicians, and study coordinators will have access to the identifiable private information. Only the study coordinator will have access to patient coding.

Please see **Data Elements Table** (Appendix 1) for a list of all elements needed to complete the aims of this trial.

Data Analysis.

[name], will be responsible for the statistical analysis of this project. He will be responsible for the statistical modeling and, along with [name], MA, will analyze all data points in our study (Oregon Research Institute).

- **Aim #1:** Aim 1 will compare differences between the two groups (EAA vs. Placebo) across experimental conditions in the change in post-TKA metabolism (synthesis & breakdown) from baseline to 1 and 2 wk post-TKA.
- **Aim #2 (trials 1 & 2):** Aim 2 will also compare measures of functional mobility with muscle cell structure (CSA) and mitochondrial function (respiration), including accelerometer and quality of life measures.

Analysis of covariance. ANCOVA will be used to answer research questions for aim 1 & 2. ANCOVA maximizes statistical power by incorporating the pretest measure as a regression-based control, reducing individual variance. Power improves as the pre-post correlations increases. Our preliminary data indicate that pre-post correlations for many key endpoints are highly correlated (e.g., muscle volume $r = .96$ for operative leg and $r = .97$ for non-operative leg; strength $r = .42$ to $.89$; stair-climb down time $r = .78$).

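### Printed detectable effects do not match 20 and 40 completers per group, and the .95 threshold does not support power for the two cell markers at 10 per condition

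*Combined protocol and SAP*

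**What the plan says.** All of this is in the Data Analysis section of the combined protocol and SAP. The Power analyses paragraph sets a two-sided type I error of .05. For Aim 1, the Power calculations paragraph starts: "For a sample size of 20 completed subjects/group (10/group for metabolic studies, however, EAA vs. Placebo = 20 total EAA and 20 total Placebo"). It puts the detectable effect without a covariate at 1.10 and continues: "with 85% power, assuming no pretest covariate, and the minimally detectable ES drops to 0.95 or 0.72 with pretest covariates of"; the two correlations meant are .50 and .75. For Aim 2 it says: "For a sample size of 40 completed subjects/group (EAA and Placebo), the proposed study can detect ESs of"; the value printed there is .79 at 85% power, falling to .68 and .52 at the same two correlations.

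The Effect sizes paragraph lists REDD1 at 1.24, SLC36A2 at 1.27 and FSR at 1.51, and averages them: "FSR calculated from mean change from baseline). The mean effect across outcomes was"; the average printed is 1.37. The Aim 1 paragraph then argues that "ESs averaged 1.37 for Cell and FSR outcomes, and all exceeded .95", and that the study "would thus have the power to detect anticipated condition effects for Cell and FSR outcomes in Aim 1 with 10 subjects per condition".

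Two further statements bear on the covariate gain. In the definition of d, "S is the pooled standard deviation, after adjusting x for pretest scores and covariates". The Analysis of covariance paragraph says: "Our preliminary data indicate that pre-post correlations for many key endpoints are highly correlated (e.g., muscle volume", followed by values for muscle volume, strength and stair descent only.

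**The concern.** Two things look wrong. First, effects of 1.10 and .79 are too large to be the limits of what 20 and 40 completers per group can detect with 85% power. Second, the .95 used to justify 10 per condition was printed for a sample twice that size and for r = .50, and no detectable effect is given for 10 per condition at all.

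The 10-per-arm case comes from the plan itself. The Aim 1 Randomization Assignments text splits each arm by biopsy week (1 or 2 weeks after surgery), and the power text names 10 per group for metabolic studies. A reader would take a non-significant single-week REDD1 or SLC36A2 result to come from a test with 85% power, when the chance of missing the anticipated effect could be about 1 in 4. For Aim 2, the reader would think the trial less sensitive than it is.

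**Working it through.** **Inputs.** Two-sided alpha .05, 85% power, 1:1 allocation (Study Design), 20 and 40 completers per group, 10 per condition for metabolic studies, r = 0, .50 and .75, and the three listed effects.

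**Formula.** Two-sample noncentral t with n per group: df = 2n − 2, less 1 when a pretest covariate is used; noncentrality = [d / √(1 − r²)] × √(n/2). The smallest detectable effect is the d at which power is .85.

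**1. The printed figures.** They are consistent with one another: 1.10 × √.75 = 0.953 and 1.10 × √.4375 = 0.728; .79 × √.75 = 0.684 and .79 × √.4375 = 0.523. The covariate step is therefore sound, and only the sample size behind the figures is in doubt.

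| n per group | r = 0 | r = .50 | r = .75 |
|---|---|---|---|
| Printed for 20 | 1.10 | 0.95 | 0.72 |
| 16 | 1.095 | 0.949 | 0.725 |
| 20 | 0.972 | 0.843 | 0.644 |
| Printed for 40 | .79 | .68 | .52 |
| 30 | 0.787 | 0.682 | 0.521 |
| 40 | 0.678 | 0.588 | 0.449 |
| 10 | 1.417 | 1.232 | 0.941 |

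Sixteen and 30 per group reproduce all six printed values to within 0.005. The normal approximation gives 0.948 at 20 and 0.670 at 40, so the choice of distribution does not explain the gap. Nor does another error rate or power level. At 20 per group, 92.5% power gives 1.103 but at 40 gives 0.770; alpha .02 gives 1.103 and 0.765. At the stated sample sizes, the printed effects have about 92% power (20 per group) and 93–94% (40 per group).

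**2. Power at 10 per condition.**

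| Outcome (d) | r = 0 | r = .50 | r needed for 85% |
|---|---|---|---|
| REDD1 (1.24) | 74.6% | 85.5% | .49 |
| SLC36A2 (1.27) | 76.6% | 87.1% | .45 |
| FSR (1.51) | 89.1% | 95.6% | none |
| The plan's threshold (.95) | 52.0% | 63.8% | about .75 |

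Exceeding .95 therefore shows adequate power at 10 per condition only if r is about .75 (power 85.7%), not the r = .50 the plan attaches to it. With no covariate gain, 85% power needs 13 per group for each cell marker and 9 for FSR.

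**3. Which column applies.** If S is the SD after pretest adjustment, the gain is already inside d and the r = 0 column applies; using r = .50 as well would count it twice. If S is unadjusted, the r = .50 column is legitimate, provided the correlation is that high. The text can be read either way.

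**4. Pooled over biopsy week (20 v 20), r = 0.** 96.9%, 97.5% and 99.6% for REDD1, SLC36A2 and FSR.

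**5. The mean.** (1.24 + 1.27 + 1.51) / 3 = 4.02 / 3 = 1.34. The Aim 2 mean does reproduce: 8.07 / 8 = 1.01.

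**The case against.** The best defence is that the conclusion is true under the plan's own lower correlation. At r = .50 and 10 per condition, all three outcomes reach 85%, and the planned analysis is ANCOVA with a pretest covariate. This stands as far as it goes. The argument offered is still not valid, and the correlation that would rescue it is not documented. The published correlations are introduced as examples, so their silence on cell outcomes does not show that none exists; it does leave the claim unsupported.

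Second, the 10-per-condition sentence states no percentage, and it is not certain that a 10 v 10 treatment test is planned. The Randomization Assignments text speaks of comparing legs at the discrete weeks, and the power text also points to 20 v 20. Both points are fair. However, 85% is the only power level in the paragraph, the list of data to be collapsed over biopsy week omits metabolic data, and the plan itself rests its conclusion on 10 per condition.

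Third, the error at 20 and 40 is harmless in direction, and the text mentions attrition. Losses of 20% and 25% would give 16 and 30, but that is an assumption: no rate is stated, and the figures are attached to completers. The Aim 2 timed tests (d = 1.03 to 1.13) exceed .79 on either calculation, so no Aim 2 conclusion changes.

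Finally, the Aim 2 recruitment text says the first part finished in 2016. A null result is best read from its confidence interval, and nothing here alters enrolment. That limits the consequence but does not make the printed figures right.

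**Conclusion.** The concern holds. The printed detectable effects do not belong to 20 and 40 completers per group: they are about 13% too high at 20 (1.10 against 0.97) and about 17% too high at 40 (.79 against 0.68). This error is conservative. The inference to 10 per condition is not valid as argued. With no covariate gain, power is 75% for REDD1 and 77% for SLC36A2. It reaches 85% only if d is unadjusted and the pre-post correlation is at least .49 and .45 respectively. FSR is adequately powered at 10 per condition on its anticipated effect, and all three outcomes have about 97% or more if the biopsy weeks are pooled. The figures assume a two-sample comparison with equal groups, equal variances and the plan's own effect sizes. This is a correction the plan should make; it does not show that the design fails.

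**What to change.** In the Power calculations paragraph:

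- Give the detectable effects for each sample size used (r = 0 / .50 / .75): 1.42/1.23/0.94 at 10 per condition, 0.97/0.84/0.64 at 20 per group, 0.68/0.59/0.45 at 40 per group. Alternatively, say that the printed values assume about 16 and 30 evaluable per group, and why.
- Replace the argument from .95 with the power at 10 per condition under both readings: 75%, 77% and 89% for REDD1, SLC36A2 and FSR with no covariate gain; 86%, 87% and 96% if r = .50 applies to an unadjusted d.
- State whether S is an adjusted or unadjusted SD, and give the pre-post correlation for the cell and FSR outcomes or say that none is available.
- State whether the metabolic treatment comparison is made within biopsy week or pooled.
- Correct the mean from 1.37 to 1.34 in both places.

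The cost is a few sentences in one section, with no extra patients and no design change. The stated case for the Aim 1 cell markers becomes less favourable; the full-group and Aim 2 figures become slightly more favourable.
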